- Visit 8: Day 84 Bronchoscopy

At visit 1, all eligible participants will give informed consent. They will then have baseline characteristics recorded, including information regarding their asthma history and symptoms, asthma control score and quality of life questionnaire (ACQ-6/mAQLQ) to assess lung function, general medical history and all current medications. Breathing tests will be performed (spirometry, fractional exhaled nitric oxide (FeNO)). A blood sample will be taken and participants will also be asked for a urine sample (pregnancy test for female participants only).

At this visit, the bronchoscopy will be discussed in more detail, and a separate bronchoscopy consent form signed. A convenient date will be arranged for both the bronchoscopy and Covid-19 test.

Visit 2: This visit is one day before the bronchoscopy and participants will have a COVID-19 test and consent for bronchoscopy.

Visit 3 and visit 8: Participants will undergo a bronchoscopy, breathing tests, have a blood test, and then the bronchoscopy with samples taken of airway cells.

Visit 4/5/6: Participants will receive a dose of benralizumab at monthly intervals during the study and will subsequently continue to receive benralizumab every 8 weeks as per standard NHS guidelines. Patients will be followed up in the NHS severe asthma clinic as their clinical condition requires. Information regarding their clinical condition will be collected from their clinical notes over the duration of the study.

Visit 7: This visit is one day before the 2nd bronchoscopy and participants will have a COVID-19 test and consent for bronchoscopy.

At all visits unless otherwise stated, the following information and samples will be collected:

Information regarding their asthma symptoms and adverse events

Asthma control score and quality of life questionnaire (ACQ-6/mAQLQ)

Breathing tests will be performed (spirometry, fractional exhaled nitric oxide (FeNO)).

A blood and urine sample (Visit 1 and 4 only) will be taken.

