7.2 Flowchart

	Screening Visit	Study visits						
Visit Number	1	2	3	4	5	6	7	8
Day		1	2	10	38	66	93	94
Full medical history, confirmation of SEA, medication review	X							
Physical examination	X	X	X	X	X	X	X	X
Current/recent medications, side effects	X		X	X	X	X	X	X
Nasal and/or throat swab for COVID-19 testing (PCR)		X					X	
Benralizumab				X	X	X		
Bronchoscopy			X					X

	Screening Visit	Study visits							
		1	2	3	4	5	6	7	8
Visit Number									
Day		1	2	10	38	66	93	94	
COVID PCR		Bronch 1	benra dose 1	benra dose 2	benra dose 3	COVID PCR	Bronch 2		
FeNO	X		X	X	X	X			X
Spirometry	X		X	X	X	X			X
Oscillometry	X		X	X	X	X			X
ACQ-6	X		X	X	X	X	X		X
mAQLQ	X		X	X	X	X	X		X
Blood	X		X	X	X	X	X		X
Urine pregnancy test (females only)	X			X					
Collection of adverse events (AE)		X	X	X	X	X	X		X

8 Subject selection

Population:

Adult patients with poorly-controlled severe eosinophilic asthma referred to Guy's Severe Asthma Centre, Guy's & St Thomas' NHS Trust, who meet NICE criteria to commence biologic therapy with benralizumab. Following review of eligibility criteria potential participants will be provided with further written information about the study in the form of the Patient Information Sheet (PIS). They will be given ample time to read this and there will be a contact telephone number in the PIS should they wish to contact the research team for further information.

This is a single centre study.

Each recruited participant will be in the study for 3 months and will attend for 8 visits including screening and informed consent. Visits will include blood, breathing tests and bronchoscopy. Participants will undergo bronchoscopy twice in a 12 week period (pre- and 12 weeks post benralizumab treatment). Processing of biological samples and data from clinical measures will be mined throughout the study period of 24 months and also when patients revert to ongoing NHS clinical care that is standard for those on benralizumab treatment for their asthma.

Retention:

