8.2 Subject exclusion criteria

1. Other severe eosinophilic lung disease including EGPA, chronic eosinophilic pneumonia and ABPA
2. Maintenance daily oral corticosteroids (prednisolone)
3. Severe bronchiectasis on CT causing daily sputum production
4. Inability to give written informed consent
5. Current smoking or >20 pack year smoking history
6. Resting oxygen saturations <94% on air
7. Any severe cardiac or other non-asthma related co-morbidity that would make bronchoscopy and/or sedation high-risk
8. Symptoms suggestive of a respiratory viral / bacterial infection within the last 3 weeks
9. Acute exacerbations of asthma requiring high dose prednisolone within the last 3 weeks
10. A change in dose of maintenance inhaled and/or oral corticosteroid dose within the last 3 weeks
11. Positive strongyloides serology following screening
12. Pregnancy or lactation
13. Hypersensitivity to benralizumab or any of the excipients

9 Study procedures

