Oscillometry is a non-invasive measure of pulmonary resistance and reactance. By measuring oscillating pressures/flow signals of moving air within the lungs, when generated at different frequencies, it provides measures of airway mechanics from different lung regions. Generally lower frequencies, in particular frequency dependent changes in resistance between 5 and 20 Hz and capacitive reactance at 5 Hz are thought to reflect changes arising in the more distal airways. Oscillometry will be performed pre- and post-bronchodilator.

Fractional nitric oxide (FeNO)

FeNO is a surrogate marker of T2-airway inflammation. FeNO will be measured using a NIOX VERO device, as specified by the manufacturer's instructions. This includes collection by controlled exhalation at the recommended controlled expiratory flow rate of 50ml/s for greater than 6 seconds.

Blood sampling

Blood will be collected for routine full blood count (including blood eosinophil and basophils), biochemistry and coagulation measurements pre-bronchoscopy. In addition plasma/ serum will be stored for proteomic/nucleic acid analyses.

Bronchoscopy

Bronchoscopy will be conducted according to established guidelines, and will be performed by respiratory physicians experienced in bronchoscopy. Participants will receive nebulised salbutamol (2.5mg) and ipratropium bromide (500mcg) prior to the procedure. Local anaesthesia will be achieved with gel applied to the nasal passages and lignocaine spray to the throat, soft palate and pharynx. Intravenous sedation using midazolam (maximum 5 mg) and alfentanil (maximum 500 mcg) will be given to achieve conscious sedation. A flexible bronchoscope will then be passed either through the nose or mouth into the lungs with additional lignocaine spray being applied to prevent coughing.

- i) Bronchial brushings will be performed using single-use brushes. Up to a total of 6 brushes will be taken.

- ii) Bronchial biopsies will be performed from the lower and middle lobes using single use forceps. Up to 6 evaluable biopsies will be taken.
- iii) Bronchoalveolar lavage (BAL): the bronchoscope will be inserted in a sub-segmental bronchi and 60ml aliquots of pre-warmed 0.9% saline will be instilled followed by gentle suction to recover lining fluid. This will be repeated up to 3 times.

At the first bronchoscopy (Visit 3) samples will be collected from the right side of the lung and at second bronchoscopy (Visit 8) samples will be taken from the left side.

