The bronchoscopy will be rescheduled if the patient has had an asthma exacerbation in the preceding 6 weeks.

Study Procedures- molecular

Epithelial brushes processing

Two brushings per patient will be stored at -80°C in RNA stabilising agent for future analysis. Four brushings will be processed for basal airway epithelial isolation by culturing in selective medium as previously described. Cultured cells, which are mainly basal epithelium, will be processed and infected/non infected with respiratory viruses including (but not restricted to) rhinovirus and SARS-CoV-2 to assess genome-wide changes, both at baseline and in their antiviral response upon benralizumab treatment. We will first set up time courses of 8, 24 and 48h given that the responses to rhinovirus and SARS-CoV-2 in bronchial epithelium differs in its dynamics, and sequence a single time point that is appropriate. We will keep RNA samples for all time points assessed for future validation purposes, together with supernatants to enable analysis of cellular mediators.

Cells infected/uninfected with virus will be subjected to RNA-seq after treatment. Top candidates based on statistical and biological significance will be validated by qPCR; western blotting/ELISA or other protein detection approaches. In the validation experiments we will also employ UV-inactivated virus as additional control. Cell culture supernatants will be collected to assess virus titres and RNA, as well as for future protein expression analyses. Cell lysates will also be stored for future protein level assessment using different platforms (proteomics; western blotting; ELISA or similar such as Luminex, O-link, etc.). Same passage cells will also be frozen for future analyses and exploratory studies detailed above.

Endobronchial biopsies

Up to 6 biopsies will be obtained:

Spatial transcriptomics: the optimal conditions of hybridization and staining will be firstly titrated in the lab using currently existing biopsy samples, to determine optimal conditions to process all samples. Biopsies will be fixed and both cryopreserved (snap frozen) as well as processed in paraffin wax for histological applications such as Visium Spatial Gene Expression protocols.

Bronchoalveolar lavage processing

An aliquot of bronchoalveolar lavage (BAL) will be stored for microbiome analysis. The BAL will then be spun to obtain cell pellets. Supernatant will be aliquoted for future analyses including microbiome, RNA and protein expression.

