12.2 Withdrawal / dropout of subjects

Treatment Regimen:

Benralizumab will be commenced according to UK NICE severe asthma guidance with 30mg sc dosing every 4 weeks for first 3 doses, followed by every 8 weeks.

No change in any background asthma medications (e.g change in ICS type or dose) is permitted during the study. Given the importance of measuring the effect of 3 doses of benralizumab following the first bronchoscopy, the subject will be excluded if they do not receive the second and third benralizumab dose at the correct time intervals (+/- 7 days for each dose) following the first benralizumab injection.

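### No pregnancy test is scheduled after Day 10, so the second sedated research bronchoscopy comes 74 or 84 days after the last one, with no written rule for a positive result

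*Protocol*

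**What the plan says.** - **Entry.** Protocol section 8.2, item 12, excludes "Pregnancy or lactation".
- **When the test is done.** Section 7.1, in the Visit 1 description, gives the urine sample's purpose as a pregnancy test for women. It then sets the timing for the whole study: "A blood and urine sample (Visit 1 and 4 only) will be taken". In section 7.2, the flowchart row beginning "Urine pregnancy test (females only" is marked at Visits 1 and 4 and nowhere else.
- **The procedure.** Section 10.3 describes both bronchoscopies in the same way: up to 6 brushings, up to 6 biopsies, lavage, and sedation. "Intravenous sedation using midazolam (maximum 5 mg) and alfentanil (maximum 500 mcg) will be given to achieve conscious sedation".
- **Checks before it.** Section 10.3 says "Blood will be collected for routine full blood count (including blood eosinophil and basophils), biochemistry and coagulation measurements pre-bronchoscopy". No pregnancy test is in that list. Section 7.1 gives Visit 7, the day before the second bronchoscopy, a COVID-19 test and bronchoscopy consent.
- **Rules during the study.** Section 10.3: "The bronchoscopy will be rescheduled if the patient has had an asthma exacerbation in the preceding 6 weeks". Section 12.2: "the subject will be excluded if they do not receive the second and third benralizumab dose at the correct time intervals". Neither mentions pregnancy.

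**The concern.** The protocol treats pregnancy as a reason not to take part, and it does not rely on one negative result, since it tests again at Visit 4. It then schedules nothing for the rest of the study, although the second bronchoscopy is still to come. That bronchoscopy is done for research, whereas benralizumab is treatment the patient has already been approved for and keeps if she leaves the study (sections 5 and 8).

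A participant who conceives after Day 10 and does not yet know it could have sedation, biopsies and lavage in a condition that would have kept her out at entry. Even if a pregnancy were found, the protocol does not say that the procedure must not go ahead. Nor does it say what follows a positive result at Visit 4.

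The first bronchoscopy is not part of this point. It follows the Visit 1 test, probably by a short interval, because section 5 limits the delay to treatment to a few weeks.

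**Working it through.** The protocol states no interval between test and procedure, so there is no figure to reproduce. The check is date subtraction and a count.

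**Inputs**
- Last scheduled pregnancy test: Visit 4, Day 10 (7.1 and 7.2).
- Second bronchoscopy: Day 84 in the visit lists of 7.1 and 9.3; Day 94 in the flowchart of 7.2.
- Visit 7: Day 83 in 7.1 and 9.3; Day 93 in 7.2.
- Planned participants: 12 (section 4).

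**Is Day 10 really the last test?** The sentence in 7.1 does not name the pregnancy test, but the Visit 1 description gives that as the purpose of the urine sample. The flowchart row has two marks, in the columns for Visits 1 and 4. Text and table agree, so this does not depend on how the table was extracted.

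**Interval** = day of second bronchoscopy − day of last test

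| Schedule | Calculation | Days | Weeks |
|---|---|---|---|
| 7.1 and 9.3 | 84 − 10 | 74 | 74/7 = 10.6 |
| 7.2 | 94 − 10 | 84 | 84/7 = 12.0 |

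The two results reflect the protocol's own disagreement over the day of Visit 8. That is a separate matter and adds no weight here. Rescheduling after an exacerbation would lengthen either interval.

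**Later visits with a pregnancy test:** Visits 5, 6, 7 and 8, so 0 of 4.

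**With a test at Visit 7:** 84 − 83 = 1 day, or 94 − 93 = 1 day.

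**Extra tests:** at most 1 × 12 = 12 for the planned participants, before repeats and replacements.

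The protocol gives neither the number of women who could become pregnant nor a conception rate, so no expected number of exposures can be calculated.

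**The case against.** The strongest reply is that periprocedural safety is handled in documents not shown here. Section 10.3 says "Bronchoscopy will be conducted according to established guidelines", section 8 refers to a standard sedation and periprocedural protocol, and section 9.1 to the trust's own bronchoscopy consent form. Any of these may require a pregnancy check before sedation. A known pregnancy could also come to light elsewhere: Visits 5 to 8 include a physical examination and a review of medication and side effects, and participants are asked about adverse events. The remaining case is therefore narrow: conception after Day 10, unrecognised by the participant and missed by any local check. The study has 12 participants, and no endpoint or error rate is affected.

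The protocol also does not say why pregnancy is excluded. Because the second test falls on the day of the first dose, it may have been placed there to guard the start of treatment.

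Most of this stands as a limit on size. It does not remove the gap. History and examination cannot be relied on to find a pregnancy the participant does not know about, which is the purpose of a test. The protocol does schedule pregnancy tests, and it uses the word only, so a site following it would conclude that none is required before the second bronchoscopy. If the tests were placed with drug treatment in mind, that would explain the schedule, but the later research procedure would still be uncovered.

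**Conclusion.** The point holds. As written, the second sedated research bronchoscopy comes 74 days (Day 84) or 84 days (Day 94) after the last scheduled pregnancy test. None of the four later visits has a test, and no rule says that a pregnancy stops the procedure.

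The conclusion is about what this protocol schedules and states. It does not assert that local practice lacks a check. The probability of harm is low and cannot be quantified from the protocol. The case for change is an avoidable exposure in a research procedure set against a very small cost. This is a participant-safety point and alters no statistical figure.

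**What to change.** 1. **Sections 7.1 and 7.2:** add a urine pregnancy test at Visit 7 for women who could be pregnant, repeated the day before any rescheduled second bronchoscopy. If the periprocedural protocol already requires a check, write it into the schedule.
2. **Section 10.3:** beside the exacerbation rule, state that the research bronchoscopy is not performed if the test is positive.
3. **Section 8 (Retention):** make clear that a pair lost for this reason is replaced. The present sentence is written for patients who decide to leave. Its aim of reaching the desired number of pairs may already cover this case, so the edit is a clarification.
4. **Optional:** a test at Visit 2 before the first bronchoscopy.

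Visit 7 is already attended in person, with a swab and consent. The cost is at most 12 urine tests for the planned participants, plus repeats after rescheduling and tests for replacements, and short wording changes. A positive result loses one paired sample, which would have to be replaced.

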7.2 Flowchart

	Screening Visit	Study visits						
Visit Number	1	2	3	4	5	6	7	8
Day		1	2	10	38	66	93	94
Full medical history, confirmation of SEA, medication review	X							
Physical examination	X	X	X	X	X	X	X	X
Current/recent medications, side effects	X		X	X	X	X	X	X
Nasal and/or throat swab for COVID-19 testing (PCR)		X					X	
Benralizumab				X	X	X		
Bronchoscopy			X					X

	Screening Visit	Study visits							
		1	2	3	4	5	6	7	8
Visit Number									
Day		1	2	10	38	66	93	94	
COVID PCR		Bronch 1	benra dose 1	benra dose 2	benra dose 3	COVID PCR	Bronch 2		
FeNO	X		X	X	X	X			X
Spirometry	X		X	X	X	X			X
Oscillometry	X		X	X	X	X			X
ACQ-6	X		X	X	X	X	X		X
mAQLQ	X		X	X	X	X	X		X
Blood	X		X	X	X	X	X		X
Urine pregnancy test (females only)	X			X					
Collection of adverse events (AE)		X	X	X	X	X	X		X

8 Subject selection

Population:

Adult patients with poorly-controlled severe eosinophilic asthma referred to Guy's Severe Asthma Centre, Guy's & St Thomas' NHS Trust, who meet NICE criteria to commence biologic therapy with benralizumab. Following review of eligibility criteria potential participants will be provided with further written information about the study in the form of the Patient Information Sheet (PIS). They will be given ample time to read this and there will be a contact telephone number in the PIS should they wish to contact the research team for further information.

This is a single centre study.

Each recruited participant will be in the study for 3 months and will attend for 8 visits including screening and informed consent. Visits will include blood, breathing tests and bronchoscopy. Participants will undergo bronchoscopy twice in a 12 week period (pre- and 12 weeks post benralizumab treatment). Processing of biological samples and data from clinical measures will be mined throughout the study period of 24 months and also when patients revert to ongoing NHS clinical care that is standard for those on benralizumab treatment for their asthma.

Retention:

The PIS will explain that the study involves 2 bronchoscopies and it is hoped that patients do not drop out of the study prior to the second bronchoscopy. We will work with our Patient Research Ambassadors to support retention. If patients decide to drop out they will continue to receive benralizumab as per the plan from the multidisciplinary team (MDT) and patients will be replaced until the desired paired sample numbers are reached. The clinical investigators are experienced in recruiting patients as well as performing bronchoscopies on patients with severe asthma and a standardised sedation and periprocedural protocol will be used to maintain consistency in sampling and patient experience.

Patients can withdraw from the study at any time. This will not affect their care or treatment within Guy's Severe Asthma Service and in particular will not affect ongoing delivery of benralizumab.

Sample Size Justification:

Based on the observed 85% responder rate to benralizumab in our centre (Kavanagh et al. CHEST 2021), statistically significant falls in FeNO observed in FeNO-high patients with benralizumab, and successful published transcriptomics studies in asthma of a similar number, we believe 12 subjects should yield at least 10 clinical responders to benralizumab. Twelve is also an achievable amount from a practical perspective to allow timely completion of this study in under 18 months from first subject in (FSI).

8.1 Subject inclusion criteria

1. Patients aged 18 and over with a diagnosis of severe eosinophilic asthma for at least the last 6 months
2. Eligible for benralizumab based on NICE criteria
3. Poorly-controlled (ACQ-6 >1.5)
4. FeNO ≥50ppb at screening despite high dose inhaled corticosteroids (at least 1000mcg BDP equivalent) +/- maintenance prednisolone
5. Adult-onset (18+) asthma in a minimum of 50% of the study subjects

8.2 Subject exclusion criteria

1. Other severe eosinophilic lung disease including EGPA, chronic eosinophilic pneumonia and ABPA
2. Maintenance daily oral corticosteroids (prednisolone)
3. Severe bronchiectasis on CT causing daily sputum production
4. Inability to give written informed consent
5. Current smoking or >20 pack year smoking history
6. Resting oxygen saturations <94% on air
7. Any severe cardiac or other non-asthma related co-morbidity that would make bronchoscopy and/or sedation high-risk
8. Symptoms suggestive of a respiratory viral / bacterial infection within the last 3 weeks
9. Acute exacerbations of asthma requiring high dose prednisolone within the last 3 weeks
10. A change in dose of maintenance inhaled and/or oral corticosteroid dose within the last 3 weeks
11. Positive strongyloides serology following screening
12. Pregnancy or lactation
13. Hypersensitivity to benralizumab or any of the excipients

9 Study procedures

9.1 Subject recruitment

Members of the patient's existing direct care team will have access to patient records for discussion at the Guy's and St Thomas' hospital NHS Trust (GSTT) severe asthma clinic meetings. Potential participants will be identified at site by the direct care team using clinic lists. Adult patients with poorly-controlled severe eosinophilic asthma referred to Guy's Severe Asthma Centre clinic at Guy's & St Thomas' NHS Trust, who meet NICE criteria to commence biologic therapy with benralizumab will be approached by the direct care team.

Following review of eligibility criteria potential participants will be provided with further written information about the study in the form of the Patient Information Sheet (PIS). They will be sent the PIS at least a week before their clinic visit and given as much time as they need to read the PIS and to ask questions. The PIS and the Informed Consent Form (ICF) will be explained in clear, simple language. They will be provided with a contact telephone number should they wish to contact the research team for further information. The patients will have as much time as they require to decide whether to take part and will be given the opportunity to go home and discuss with family/friends if they want to.

The bronchoscopy procedure will also be discussed in detail prior to obtaining consent. The asthma direct care team at GSTFT are integrated with the research team and these activities will be completed by both teams.

Informed Consent:

The process for obtaining participant informed consent will be in accordance with the REC guidance, and GCP and other regulatory requirements that might be introduced.

The chief investigator and/or the direct care team will conduct the informed consent process by explaining to the participant the nature of the study; its purpose; the procedures involved; the expected duration; the potential risks and benefits involved; and the fact that participation is completely voluntary and consent may be withdrawn at any time with no consequences for their subsequent medical care.

Participants will also be asked to review and sign a standard bronchoscopy consent form currently used by the respiratory department as per trust policy

The CI/PI/delegate and the participant or other legally authorised representative shall both sign and date the Informed Consent Form before the person can participate in the study.

The participant will keep a copy of the PIS and a signed and dated Consent Form. The original will be retained in the Trial Master File. A second copy, along with the PIS, will be filed in the participant's medical notes and a signed and dated note made in the notes of when the PIS was provided and that informed consent was obtained for the study.

The decision regarding participation in the study is entirely voluntary. The investigator or their nominee shall emphasize to the participant that consent regarding study participation may be withdrawn at any time without penalty or affecting the quality or quantity of their future medical care, or loss of benefits to which the participant is otherwise entitled.

Participation in the study is voluntary and recruited patients will not be paid.

Participants will also be made aware of and consent to the fact that their GP will be informed of their participation. Each participant will authorise in writing that portions of their medical records and source data related to the project may be reviewed by a monitor, an auditor or a regulatory inspector, in accordance with applicable regulatory requirements. They will be made aware that Data protection will be handled in compliance with UK law.

